## 1. Version History

Version	Summary of Changes	Author(s)/Title
1.0	• Not Applicable, New Document	[REDACTED]

## 2. List of Abbreviations and Definitions of Terms

Abbreviation	Definition
AE	Adverse Event
CIP	Clinical Investigational Plan
CL	Closed-Loop
DD	Device Deficiency
DMC	Data Monitoring Committee
ECAP	Evoked Compound Action Potential
ECHO-MAC	Electrically evoked compound action potentials human observation Medtronic Algorithm Comparison study
ECAP	Evoked Compound Action Potential
IDE	Investigation Device Exemption
ITT	Intent-to-treat
IRB	Institutional Review Board
MI	Multiple Imputation
MedDRA	Medical Dictionary for Regulatory Affairs
OL	Open-Loop
PASS	Power Analysis & Sample Size
SAP	Statistical Analysis Plan
SAS	Statistical Analysis System
SCS	Spinal Cord Stimulation

## 3. Introduction

This Statistical Analysis Plan (SAP) is based on the Electronically evoked compound action potentials human observation Medtronic Algorithm Comparison (ECHO-MAC) Study Clinical Investigational Plan (CIP). The SAP presents the details of the methods to be used to analyze and report the study results of the ECHO-MAC study, protocol number MDT19024.

## 4. Study Objectives

### 4.1 Primary Objective

To demonstrate that the proportion of subjects with a reduction in overstimulationa sensation with spinal cord stimulation (SCS) using a closed-loop (CL) algorithm compared with SCS in open-loop (OL) exceeds a performance goal of 50%.

a Overstimulation is defined as an uncomfortable sensation of stimulation (intense tingling, shocking, jolting) brought about by protocol-prescribed activities (i.e. coughing, back arch, performing Valsalva maneuver). This overstimulation sensation is transient and reversed by the subject's returning to a neutral position.

- [REDACTED]
- [REDACTED]

## 4.3 Safety Assessment

All device-related, therapy-related, and procedure-related adverse events and device deficiencies will be characterized from the start of the in-clinic testing until study exit.

## 5. Investigation Plan

[figure not shown]
This is a prospective, multi-center, randomized, single-blind, cross-over, non-significant risk Investigation Device Exemption (IDE) study. This study will be conducted in the United States with up to 15 sites; each site will contribute up to 10 enrolled subjects. Up to 60 subjects are expected to be enrolled in the study to allow for at least 42 subjects for analysis.

The expected total study duration is approximately 6 months. The duration of a subject's participation is approximately 2 weeks from enrollment, although this may vary depending on when enrollment occurs relative to the SCS device trial.

[Figure 5-1](#) is a flow diagram of how subjects will complete the study. Subjects will be required to come into the clinic for 2 study visits, although they could occur on the same day:

- Enrollment
- In-clinic Testing Visit

**Figure 5-1: Study Visit Diagram**

Subject randomization will occur after a clear, measurable ECAP [REDACTED]  
[REDACTED] is verified and the algorithm is setup. Subjects will be randomized to the sequence of receiving OL and CL in-clinic testing. Subjects will be blinded to the settings tested. The In-clinic Testing Visit is expected to last up to 3 hours and subjects will be discontinued at the end of the visit.

## 6. Determination of Sample Size

The primary endpoint is to demonstrate that the proportion of subjects with a reduction in overstimulation sensation with SCS using a CL algorithm compared with SCS in OL exceeds 50%. PASS 2020 Group-Sequential Tests for One Proportion in a Fleming Design module was used to calculate the sample size. With a null proportion of 50%, an alternative proportion of 75%, and one interim analysis at 70% of the total sample size, 42 subjects are needed to achieve more than 90% power with a one-sided alpha = 0.025 test.

To account for a 30% attrition between enrollment and randomization, up to 60 subjects may be enrolled into the study. A 30% attrition rate was based on historical attrition rates from similar studies, as well as to account for the subjects who don't have a clear, measurable ECAP.

## **7. Statistical Methods**

### **7.1 Study Subjects**

#### **7.1.1 Disposition of Subjects**

Subject disposition will be summarized by study visit in a flow diagram. Discontinuation will be summarized by visit and discontinuation reasons will be provided.

#### **7.1.2 Clinical Investigation Plan (CIP) Deviations**

All CIP deviations will be summarized by the type of deviation. Details of CIP deviations that affect scientific integrity and subject safety may be presented.

#### **7.1.3 Analysis Sets**

Enrolled Analysis Set: includes all consented subjects.

Intent-to-treat (ITT) Analysis Set: includes all subjects who are randomized.

Completer Analysis Set: includes subjects who are randomized and provide assessment for overstimulation sensation at both the OL and CL in-clinic testing periods.

## **7.2 General Methodology**

Two formal analyses are planned for this study: one interim analysis will occur [REDACTED] and one final analysis will occur after all subjects complete the study. The Interim Analysis is described in [7.8](#). A final report will be prepared once all data collection has ended and all subjects have completed the study and have been exited.

General descriptive statistics for categorical and continuous variables will be used. Categorical variables will be summarized as counts and percentages; continuous variables will be presented using counts, mean, standard deviation, median, quartiles and range as applicable.

Data analysis will be performed by Medtronic-employed statisticians or designees. A validated statistical software package (e.g., SAS version 9.4 or higher) will be used to analyze the study results.

## **7.3 Center Pooling**

There is no a priori provision to exclude any sites from the analysis. The data from all sites will be pooled for analysis. To reduce the possibility of atypical results from a site overly influencing the combined results, no more than 10 subjects will be enrolled at each site. The per-study site enrollment cap may be increased upon Sponsor approval.

A poolability analysis to test for a treatment difference among sites is described in the supporting analyses of the primary objective in [7.9.1.7.1](#).

## 7.4 Handling of Missing, Unused, and Spurious Data and Dropouts

Missing data are a potential source of bias when analyzing study data. Selection of subjects, treatment of subjects, and evaluation of study data are potential sources of bias. Methods incorporated in the study design to minimize potential bias include (but are not limited to):

- Subjects' in-clinic testing sequences are randomized with stratification at each site. This is to ensure subjects get equal opportunities to start with either OL or CL testing.
- Subjects are blinded to the OL or CL testing settings. This is to ensure that the knowledge of testing settings is not going to influence the subjects' assessment of overstimulation sensation.
- Missing data are a potential source of bias when analyzing study data. A rigorous study design and execution will help prevent the incidence of missing data from occurring. All efforts will be made to ensure subject follow-ups are completed with limited attrition to ensure interpretability of study results.
- To reduce the possibility of atypical results from a site overly influencing the combined results, the maximum number of subjects to be enrolled at a single study site is limited to 10 and cannot be increased without prior sponsor approval.

The primary analysis of the primary objective will include subjects who are randomized (ITT Analysis Set) and if, across all subjects, more than 5% of the average intensity scores for either the OL or CL period are missing, will utilize the Multiple Imputation (MI) methodology for missing data. MI will only be used for the analysis of the primary objective and is not planned to be utilized for any other analyses.

Prior to the use of MI, the distributions of the continuous average stimulation intensity variables will be assessed for normality (using the Shapiro-Wilk test) to determine if transformation of non-normal variables ( $p \leq 0.05$ ) may be considered, or if a different imputation specification that is more appropriate for non-normal data may be used.

[REDACTED]

Following

imputation, the objective will be evaluated using MI analysis method.

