#### 7.9.1.2 Endpoint definition and derivation

For every overstimulation sensation brought about by 3 to 5 protocol-prescribed activities, subjects will rate the intensity of the sensation in the following 5-point Likert scale:

- No overstimulation sensation (code=0)
- Weak overstimulation sensation (code=1)
- Moderate overstimulation sensation (code=2)
- Strong overstimulation sensation (code=3)

- Very strong overstimulation sensation (code=4)

The average of all non-missing intensity scores during the OL and CL period will be calculated for each individual subject. If there is at least one non-missing intensity score for a period, the subject's data will be used without imputing values. If a subject is missing all intensity scores for a period, then that subject has a missing average intensity score for that period. If, across all subjects, more than 5% of the average intensity scores for either the OL or CL period are missing, then MI will be utilized as specified in 7.4. If the average intensity score during the CL period is less than that from the OL period, the subject is considered as a subject with a reduction in overstimulation sensation during CL vs. the OL period. The proportion of subjects with a reduction in overstimulation sensation among subjects who have in-clinic testing is the primary endpoint.

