### **7.9.1.5 Analysis Methods**

The proportion of subjects with a reduction in overstimulation sensation during CL compared to the OL period will be calculated and evaluated with a one-sided 97.5% confidence lower bound. This proportion will be tested against 50% using a binomial exact test. The confidence lower bound needs to be greater than 50%, or equivalently, the p-value needs to be less than 0.025 to declare a study success. This implies that among the estimated total 42 randomized subjects, 28 subjects or more need to have a reduction in overstimulation sensation for the study to be considered a success.

Two sensitivity analyses will be performed if there is any missing primary endpoint data. One sensitivity analysis, a tipping point analysis, will be performed using the ITT Analysis Set. This analysis will be performed on the primary endpoint by displaying the full range of proportions on the potential impact of missing data by running an analysis assuming all missing values are a higher average stimulation intensity value for CL vs OL (worst case) to all missing values are a lower average stimulation intensity value for CL vs OL (best case).

Another sensitivity analysis will be performed on the primary endpoint by including only the subjects who finish the in-clinic testing and provided the scoring of overstimulation sensation for both OL and CL periods (Completer Analysis Set).

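### Does the Shapiro-Wilk check before imputation in SAP 7.4 bias the primary endpoint by mishandling subjects whose closed-loop and open-loop averages tie?

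*SAP*

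**What the plan says.** SAP 7.9.1.2 builds the endpoint from integer ratings. "For every overstimulation sensation brought about by 3 to 5 protocol-prescribed activities", the subject gives a code from 0 to 4, and the codes are averaged within each period. "If there is at least one non-missing intensity score for a period", that period's average is used as it stands. The responder rule is a strict inequality: "If the average intensity score during the CL period is less than that from the OL period", the subject counts as reduced. A tie is therefore not a reduction.

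Multiple imputation applies only when more than 5% of the averages in either period are missing. SAP 7.4 then says that "the distributions of the continuous average stimulation intensity variables will be assessed for normality (using the Shapiro-Wilk test"). At p of 0.05 or less, a transformation may be considered, "or if a different imputation specification that is more appropriate for non-normal data may be used". A redacted block follows directly.

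SAP 7.9.1.5 adds two sensitivity analyses if any primary endpoint data are missing: a completer analysis, and a tipping point analysis "displaying the full range of proportions on the potential impact of missing data", from worst case to best case.

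**The concern.** The averages are called continuous but lie on a coarse, bounded grid. The endpoint depends on the sign of CL minus OL, and exact equality counts against success. Shapiro-Wilk looks at the shape of each average separately and carries no information on how often the two coincide. If the averages pass and are then imputed by a normal model without rounding, ties have essentially zero probability. Subjects who would have tied are split between reduced and not reduced, which usually favours CL. A transformation does not cure this.

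The two *may* options also leave the imputation method for the only confirmatory endpoint to be settled after the data are seen. At the boundary one subject decides the trial, so even a small upward error might matter.

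**Working it through.** **Inputs from the SAP.** N = 42, null 50%, alternative 75%, one-sided alpha 0.025 (section 6); success at 28 of 42 (7.9.1.5); the 5% trigger, the 0 to 4 codes and 3 to 5 activities (7.9.1.2). The SAP gives no score distribution, tie rate or missing rate, so steps 3 to 5 are simulations under assumed distributions.

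**1. The plan's own figure.** Exact binomial, leaving the interim look aside: P(X ≥ 28 | 42, 0.50) = 0.0218 and P(X ≥ 27) = 0.0442. Power at 75% is 0.919. The lower 97.5% bound for 28/42 is 0.5045. The cut-off of 28 and power above 90% are reproduced.

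**2. When imputation runs.** 2/42 = 4.8% and 3/42 = 7.1%, so at least 3 averages must be missing in a period. With chance q of missing a period, P(X ≥ 3) = 1 − Σ C(42,k) q^k (1−q)^(42−k) over k = 0, 1, 2. This gives 0.9% at q = 1%, 5.2% at q = 2% and 35% at q = 5%. For either period it is at most double. The planned loss, "To account for a 30% attrition between enrollment and randomization", falls before randomization and does not feed this trigger.

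**3. Does the check detect ties?** No. In four assumed scenarios the tie share in passing versus failing samples was 13.1% vs 12.9%, 8.4% vs 8.2%, 19.0% vs 19.1% and 21.5% vs 21.8%. That comparison is weak, because within one fixed distribution the tie share hardly varies. The comparison across distributions is better: the test rejected about 100% of samples when ties were 0.8 to 1.6% (CL near the floor) but only 14% when ties were 27.5%.

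**4. Error in the probability of reduction, per imputed subject (percentage points).**

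| Method | Eight scenarios, 8–22% ties | Skewed CL−OL difference |
|---|---|---|
| Normal, unrounded (passing samples) | +3 to +12 | −13 to −21 |
| Normal, rounded and bounded to the grid | −2 to +2 | not run |
| Predictive mean matching | −2 to +1 | −10 to −14 |
| Penalised logistic on the binary outcome | −3 to +1 | −2 to −7 |

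A separate set of scenarios with 9 to 16% ties gave about +4 to +7 for unrounded normal draws and about −3.5 to +1 for the other three methods.

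**5. Effect on the trial.** With 3 imputed, the shift is 3 × 0.03 = 0.09 to 3 × 0.12 = 0.36 responder (0.08 to 0.35 before the errors are rounded). With 39 observed, 3 imputed and Rubin pooling with a Wald bound (assumed), the chance of success is:

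| True proportion | Error 0 | +5 points | +10 points |
|---|---|---|---|
| 50% | 2.5% | 2.6% | 2.7% |
| 65% | 49% | 52% | 56% |
| 75% | 94% | 95% | 96% |

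**The case for a change.** The strongest case for a change is a tie-heavy trial. With a true proportion of 50%, ties of 26 to 33% and 3 to 6 CL averages missing, unrounded normal imputation gave missing subjects a 0.63 to 0.67 chance of reduction, against 0.505 to 0.513 under predictive mean matching. The shift was 0.010 to 0.024 in the proportion, or 42 × 0.010 = 0.4 to 42 × 0.024 = 1.0 subject. The chance that the pooled proportion reached 28/42 was 2.4 to 4.2%, against 1.8 to 2.4%. A sensitivity analysis would expose this but would not correct the primary result, and naming one method in advance costs only a sentence.

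What stands is that the check is uninformative about ties and that the visible wording leaves a choice open. The 4.2% carries less weight. It needs 6 of 42 averages missing and about a third of subjects tied, and it applies the 28/42 cut to the pooled proportion without the between-imputation variance. With Rubin-Wald pooling and 6 missing, the rate at a true 50% was 1.5%, 1.9% and 2.6% for errors of 0, +5 and +10 points.

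Nor is any replacement clearly better. Logistic imputation does no better than rounding, and near a true proportion of 0.85 its error (−3.5) is about the size of the one it would cure (+4.1). Predictive mean matching errs by −10 to −14 under skew. Imputing the binary outcome would also mean rewording 7.9.1.2 and 7.9.1.6, which speak of missing averages.

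**Conclusion.** No change follows. The check does not address ties, but it was not written to; it asks whether a normal-theory imputation suits the averages, and its failing branch already permits a method for non-normal data, such as predictive mean matching. An error in the primary result would need unrounded normal draws, and the SAP nowhere prescribes them. The model, rounding and bounds may well sit in the redacted block, whose absence from view is not a gap in the plan. Failing that, an analyst who sees scores on a 0 to 4 grid can round and bound the draws, which leaves an error of −2 to +2 points.

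What remains is a minor matter of detail in two *may* options. Its size is below 0.4 responder with 3 imputed and 8 to 22% ties, up to about one subject with 6 imputed and very frequent ties, and of unstable sign. It arises only after the 5% trigger, which is unlikely if missing a period is rare: testing is a single visit of up to 3 hours, and one rating suffices for a period average. All error sizes rest on assumed score distributions and, in most runs, data missing completely at random. The arithmetic on 42, 28 and the trigger does not depend on those assumptions.

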## 7.5 Adjustments for Multiple Comparisons

As there is one primary objective, adjustment for multiple endpoints is not required.

## 7.6 Demographic and Other Baseline Characteristics

Demographics and Baseline characteristics will be summarized for the Enrolled Analysis Set and the ITT Analysis Set separately, and may include:

- Age, sex, and race
- Primary Indication
- Medical history

- Medication information
- History of treatments

## 7.7 Treatment Characteristics

Relevant characteristics from the in-clinic test will be summarized and described.

## 7.8 Interim Analyses

One planned interim analysis will be conducted under the auspices of the data monitoring committee (DMC) assigned to this study. The DMC will disseminate interim results only if necessary. Any such dissemination will be documented and described in the final study report. Study sites will not receive information about interim results unless they need to know for the safety of their subjects.

## 7.9 Evaluation of Objectives

### 7.9.1 Primary Objective

The primary objective is to demonstrate that the proportion of subjects with a reduction in overstimulation sensation with SCS using a CL algorithm compared with SCS in OL exceeds a performance goal of 50%.

#### 7.9.1.1 Hypothesis

It is hypothesized that the proportion of subjects with a reduction in overstimulation sensation during CL compared to the OL period exceeds a performance goal of 50%. The null ( $H_0$ ) and alternative ( $H_A$ ) hypotheses are:

$$H_0: p \leq 50\%$$

$$H_A: p > 50\%$$

Where  $p$  is the proportion of subjects with a reduction in overstimulation sensation during CL compared to the OL period.

#### 7.9.1.2 Endpoint definition and derivation

For every overstimulation sensation brought about by 3 to 5 protocol-prescribed activities, subjects will rate the intensity of the sensation in the following 5-point Likert scale:

- No overstimulation sensation (code=0)
- Weak overstimulation sensation (code=1)
- Moderate overstimulation sensation (code=2)
- Strong overstimulation sensation (code=3)

- Very strong overstimulation sensation (code=4)

The average of all non-missing intensity scores during the OL and CL period will be calculated for each individual subject. If there is at least one non-missing intensity score for a period, the subject's data will be used without imputing values. If a subject is missing all intensity scores for a period, then that subject has a missing average intensity score for that period. If, across all subjects, more than 5% of the average intensity scores for either the OL or CL period are missing, then MI will be utilized as specified in 7.4. If the average intensity score during the CL period is less than that from the OL period, the subject is considered as a subject with a reduction in overstimulation sensation during CL vs. the OL period. The proportion of subjects with a reduction in overstimulation sensation among subjects who have in-clinic testing is the primary endpoint.

### **7.9.1.3 Performance Requirements**

The null hypothesis will be rejected if the one-sided 97.5% lower confidence bound is greater than 50% or, equivalently, if the p-value for the hypothesis test is less than 0.025.

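### Does the unqualified p < 0.025 success rule let the interim look push the one-sided type I error above 2.5%?

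*SAP*

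**What the plan says.** - **Section 6** sizes the trial with the Fleming group-sequential module for one proportion: null 50%, alternative 75%, one-sided alpha 0.025, 42 subjects, power above 90%, and "one interim analysis at 70% of the total sample size".
- **Section 7.2**: "Two formal analyses are planned for this study: one interim analysis will occur", after which the text is redacted, and a final analysis once all subjects have completed.
- **Section 7.8**: "One planned interim analysis will be conducted under the auspices of the data monitoring committee (DMC) assigned to this study". The rest of the visible text deals with who may see interim results. It gives no boundary and does not say whether the null hypothesis can be rejected early.
- **Section 7.9.1.3**: "The null hypothesis will be rejected if the one-sided 97.5% lower confidence bound is greater than 50" percent, or equivalently if p is below 0.025. No analysis is named.
- **Section 7.9.1.5** specifies an exact binomial test, says "the p-value needs to be less than 0.025 to declare a study success", and draws the consequence that "among the estimated total 42 randomized subjects, 28 subjects or more need to have a reduction in overstimulation sensation".
- **Section 7.5**: "As there is one primary objective, adjustment for multiple endpoints is not required". It does not mention repeated looks.
- Section numbering goes from 7.9.1.3 straight to 7.9.1.5, and blacked-out text follows 7.9.1.6.

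**The concern.** A threshold of p < 0.025 is a single-look rule. Used in full at an interim and again at the end, it gives the null hypothesis two chances to be rejected, and the overall error rises above the nominal level. Here two formal analyses are planned, the rejection rule names neither, the multiplicity section covers endpoints only, and the visible interim section gives no boundary. Read literally, 21 responders at the interim would already satisfy p < 0.025.

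That could decide the result. If the true proportion is 50%, a trial with exactly 21 interim responders would go on to miss 28 of 42 with probability P(Bin(13, 0.5) ≤ 6) = 0.50 for an interim at 29, or P(Bin(12, 0.5) ≤ 6) = 0.61 for an interim at 30. If 21 counted as success, the trial would exceed the error rate it was designed for.

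**Working it through.** **Inputs.** From Section 6: null 0.50, alternative 0.75, one-sided alpha 0.025, N = 42, interim at 70%. From Section 7.9.1.5: exact binomial test, final cut 28. Since 0.70 × 42 = 29.4 and the rounding is not stated, the interim size n1 is taken as 29 and as 30.

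**1. The plan's own cut, final look only.** Under p = 0.5, P(X ≥ 28 | 42) = 0.0218 and P(X ≥ 27 | 42) = 0.0442. So 28 is the smallest count with p < 0.025, as Section 7.9.1.5 says. Power at 75% is P(X ≥ 28 | 42) = 0.919.

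**2. The literal two-look reading.** With interim cut r1 and final cut 28:

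error = P(X1 ≥ r1) + Σ over x < r1 of P(X1 = x) · P(X2 ≥ 28 − x),

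where X1 ~ Bin(n1, 0.5) and X2 ~ Bin(42 − n1, 0.5). The smallest interim count with p < 0.025 is 21 in both cases (p = 0.0121 at 29, p = 0.0214 at 30).

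| n1 | r1 | Interim part | Final part | Overall error |
|---|---|---|---|---|
| 29 | 21 | 0.0121 | 0.0147 | 0.0268 |
| 30 | 21 | 0.0214 | 0.0111 | 0.0325 |

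So the inflation would be real if this were the procedure.

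**3. The design that Section 6 names.** The standard Fleming success cut is round(n·p0 + 1.96·√(N·p0·(1 − p0))) + 1, with n the number of subjects at that stage and 1.96·√(42 × 0.25) = 6.351:

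- n = 29: 14.5 + 6.351 = 20.851, rounds to 21, cut 22
- n = 30: 15 + 6.351 = 21.351, rounds to 21, cut 22
- n = 42: 21 + 6.351 = 27.351, rounds to 27, cut 28

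The matching futility cut is round(n1·p̃ − 1.96·√(N·p̃·(1 − p̃))), with p̃ = (√(N·p0) + 1.96·√(1 − p0))² / (N + 1.96²) = 0.777. This gives 17 of 29 or 18 of 30. Step 2's formula with r1 = 22, dropping the terms at or below the futility cut where it binds, gives:

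| n1 | Futility | Error at 50% | Power at 75% |
|---|---|---|---|
| 29 | none | 0.0041 + 0.0187 = 0.0228 | 0.921 |
| 29 | stop at ≤ 17 | 0.0041 + 0.0174 = 0.0214 | 0.911 |
| 30 | none | 0.0081 + 0.0162 = 0.0243 | 0.922 |
| 30 | stop at ≤ 18 | 0.0081 + 0.0143 = 0.0224 | 0.909 |

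All four errors are below 0.025 and all four powers exceed 90%, as Section 6 states.

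**4. Comparison with the text.** The only count in the plan, 28 of 42, is both the single-look exact cut (step 1) and the Fleming final-stage cut (step 3). The count of 21 appears nowhere in the plan, and it would depart from the design in Section 6, which gives 22.

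**The case for a change.** The best case on the other side is that the wording itself is loose. Section 7.9.1.3 contains no 28-of-42 example and no restriction to the final analysis. In Section 7.9.1.5 the count illustrates the rule and does not expressly limit it to one look. Section 7.2 calls the interim formal, and Section 6 builds it into the sizing for the primary proportion, so one cannot simply assume that it tests nothing. Even if a separate interim boundary exists, an unqualified rule sits awkwardly beside it.

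What stands is that a few words tying the rule to the final analysis would be tidier. That is a matter of wording. The rule can be called unqualified only as far as the visible text goes, and the text is cut where a qualification would naturally be: after the interim is announced in Section 7.2, and in the unshown 7.9.1.4 between the rejection rule and the analysis methods. The protocol is not at hand either. Section 7.5 does not help the objection, because it is correct about endpoints and makes no claim about looks.

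A second argument is that "up to 60 subjects may be enrolled into the study", so the final number may not be 42. With an interim cut of 22, no futility stop and p < 0.025 at the end, the overall error does pass 0.025 at some larger sizes: 44, 51 and 58 for an interim at 29 (maximum 0.0259), and 44, 49, 51, 56 and 58 for an interim at 30 (maximum 0.0281). But 60 is the enrolment ceiling before 30% attrition: 60 × 0.70 = 42. These excesses also presuppose a boundary and a no-futility policy that the visible text does not give. They cannot be charged to this plan.

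**Conclusion.** The concern does not hold. The errors of 0.0268 and 0.0325 are correctly calculated, but they belong to a procedure that the SAP does not describe: full-level testing at both looks with success at 21. The rule it does state, worked out as 28 of 42, has an error of 0.0218 on its own. Inside the Fleming design of Section 6 the overall error is 0.0214 to 0.0243, with power of 90.9% to 92.2%. Both possibilities, an interim that can reject under that design and one that cannot, keep the planned 0.025.

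This rests on three assumptions: an interim at 29 or 30 subjects, a final analysis of 42, and interim boundaries that follow the standard Fleming formula, since the software output is not shown. The interim policy cannot be read from the visible text, but because of the redactions and the unseen protocol that is not evidence that it is missing.
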